### **8.2      Analysis of the secondary endpoints**

- **Apoptotic markers.** Caspase 3 staining (and/or TUNEL assay results) will be expressed as the mean staining percentage in tumor samples, and reported separately for each treatment group. Standard deviations, 95% confidence intervals, and ranges will also be reported where appropriate. Means will be compared across treatment arms using two-way ANOVA.
- **Proliferation markers.** Ki-67 staining will be expressed as the mean staining percentage in tumor samples, reported separately for each treatment arm. Standard deviations, 95% confidence intervals, and ranges will also be reported where appropriate. Means will be compared across treatment arms using two-way ANOVA.
- **Pathological complete responses (pCR).** This will be defined as an absence of tumor identification on standard histological analysis of the resected prostate specimens. The proportion of patients achieving a pCR will be compared between treatment arms using the Mantel-Haenszel test.

- **PSA response rates.** This will be defined as an undetectable PSA (<0.1 ng/mL) at 3 months after prostatectomy. The proportion of patients achieving a PSA response will be compared between treatment arms using the Mantel-Haenszel test.

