### Exploratory Objectives

- (1) To evaluate genome-wide mRNA expression changes in prostate cancer induced by LDE225 exposure.

The objectives and related endpoints are summarized in the [Table](#) below.

	Objective	Endpoint	Analysis
Primary	Pharmacodynamic effect of LDE225 on prostate tissue	50% reduction in Gli1 mRNA expression comparing pre-operative prostate biopsies to radical prostatectomy specimens	qRT-PCR performed on pre-operative tumor biopsy specimens and tumor from RP specimens. Comparison performed within and between treated and untreated groups. Correlation of Gli1 levels to pre-operative Gli1 expression.
Secondary	
 
-Pathological effect on localized high-risk cancer
 
-To determine whether pre-surgical treatment with LDE225 diminishes the risk of PSA recurrence following prostatectomy
 
-To evaluate drug-related toxicities including peri-operative complications
 
	
 
-Assessment of tumor stage and grade (predicted versus actual) and changes in proliferation and apoptosis
 
-PSA <math>\geq 0.2</math> ng/ml at 3 months following prostatectomy
 
-Length of surgery, intraoperative blood loss, length of hospital stay, rates of post-operative complications (infection, wound breakdown, deep vein thrombosis, within 90 days from surgery)
 
	
 
-Routine pathologic analysis. Additionally, semi-quantitative IHC for Ki-67 and cleaved caspase-3. Comparison performed within and between treated and untreated groups.
 
-Routine serum ELISA for PSA
 
-Comparison of routinely collected intraoperative and post-operative data between treated and untreated groups
 

Exploratory	Evaluate genome-wide mRNA expression changes in prostate cancer induced by LDE225 exposure	Gene expression analysis on biopsy and prostatectomy tissue using the Affymetrix GeneChip Human Exon 1.0ST Array	Differential gene expression analysis and analysis of functional annotation comparing biopsy and prostatectomy specimens both between and within groups

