### 3      **Investigational Plan**

#### 3.1      **Overview and study design**

This pharmacodynamic/phase 0 trial is designed as a randomized two-arm (LDE225 vs. observation groups) open-label prospective clinical trial in men with localized high-risk prostate cancer undergoing radical prostatectomy.

Activation of the Hedgehog pathway is most reliably indicated by increased expression of the *GLI1* transcription factor. Quantitative RT-PCR (qRT-PCR) provides the most reliable means to assess changes in *GLI1* expression upon exposure to drug and will be used as our primary readout. Our intent will be to examine the fold change in *GLI1* expression in each man following exposure to drug (comparing pre-operative needle biopsy tissue to surgical tissue obtained from the same man's prostatectomy specimen). Because the effects of surgery and fluctuations in hedgehog signaling in the prostate are unknown, *GLI1* expression will also be compared between biopsies and prostatectomy specimens for men without drug exposure. As treatment with LDE225 may alter the gene expression of other Hedgehog pathway members and affect separate signaling pathways, as an exploratory goal, we will perform genome-wide expression analysis using the GeneChip Human Exon 1.0ST Array (Affymetrix) and will confirm fluctuations in selected genes of interest.

High-risk patients will be identified based on their core-needle biopsy features, PSA levels, and clinical stage. Eligible men (NCCN high-risk (Gleason sum  $\geq 8$ , or PSA  $>20$  or clinical stage  $\geq T3$  with no evidence of metastatic disease) will undergo a repeat prostate biopsy at Johns Hopkins with multiple (up to 12) cores taken from the area of their primary lesion. This tissue will be frozen fresh and used for analysis of *Gli1* mRNA expression and array analysis as well as mounted for pathological analysis and IHC analysis of proliferation (Ki-67) and apoptosis (cleaved caspase-3) markers.

[figure not shown]

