## **6.2 Assessments**

### **6.2.1 Efficacy assessments**

The primary measures of efficacy in this trial are pharmacodynamic measured by the change in *Gli1* expression by qRT-PCR. In addition, efficacy will also be evaluated in secondary endpoints which will compare tumor stage, grade, surgical margin rates and tumor proliferation / apoptosis between treatment and observation arms. The proportion of patients with undetectable PSAs at three months will also be assessed in the two groups.

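### Section 8.2 prescribes a two-way ANOVA for Ki-67 and caspase-3 but names one factor and no tested term; a baseline-adjusted ANCOVA would settle the between-arm test

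*Combined protocol and SAP*

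**What the plan says.** Section 8.2 uses one sentence for both markers: "Means will be compared across treatment arms using two-way ANOVA". The input is a mean staining percentage by arm; for apoptosis, "Caspase 3 staining (and/or TUNEL assay results) will be expressed as the mean staining percentage in tumor samples". The section does not say whether the samples are biopsy tissue, prostatectomy tissue or both. It names no second factor, tested term, patient term or significance level for these markers.

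Other sections describe the intended comparison:

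- The objectives table in section 2 gives the endpoint as "Assessment of tumor stage and grade (predicted versus actual) and changes in proliferation and apoptosis", with "Comparison performed within and between treated and untreated groups".
- Section 6.2.1 lists "tumor proliferation / apoptosis between treatment and observation arms" among the efficacy comparisons.
- Section 3.1 plans a repeat biopsy before treatment, with "multiple (up to 12) cores taken from the area of their primary lesion". That tissue is to be "mounted for pathological analysis and IHC analysis of proliferation (Ki-67) and apoptosis (cleaved caspase-3) markers".
- Section 3.1 later compares biopsy with prostatectomy tissue on a different score, intensity multiplied by the percentage of cells. There it calls the biopsy the diagnostic one.
- Section 3.1.4 randomizes 1:1 and names no stratification factor.

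**The concern.** No stratum is available to be the second factor, and both markers are measured before and after drug. Specimen (biopsy or prostatectomy) is therefore the natural candidate, but the text does not confirm it. Even if it did, the model yields two different between-arm tests with different targets, and 8.2 chooses neither.

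Secondary objective 1 (more apoptosis, less proliferation) rests on these tests in 22 men. An unspecified term can cost power. An omitted patient term distorts the error rate. Choosing the term after seeing the data inflates the error rate further.

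**Working it through.** **The plan's own figure.** The only sample size stated is for the primary endpoint in 8.1: 10% against 70%, two-sided alpha 0.10, power 80%.

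- Uncorrected: n = [1.645·√(2·0.4·0.6) + 0.842·√(0.1·0.9 + 0.7·0.3)]² / 0.6² = 7.1.
- Continuity-corrected: (7.1/4)·[1 + √(1 + 4/(7.1·0.6))]² = 10.2, so 11 per arm.

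The stated figure is reproduced, and nothing below alters it.

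**Inputs for the markers.** From the documents: 11 per arm (3.1.4, 8.1). Assumed, because the documents give none: normal data, SD 1 at each specimen, within-man correlation ρ, and a true drug effect d on post-drug tissue only. A two-sided 0.05 level is borrowed from the Gli1 comparison in 6.2.4.

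**What each reading estimates.** Randomization makes the expected pre-drug difference zero.

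- (a) Arm main effect of an arm × specimen ANOVA: (0 + d)/2 = d/2.
- (b) Arm × specimen interaction, which is the between-arm difference in change: d − 0 = d.
- (c) Prostatectomy tissue only: d.
- ANCOVA of the prostatectomy value adjusted for biopsy: d.

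In simulation with d = 1.2, (a) averages 0.60 and the other three average 1.20.

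**Precision.** The relevant per-man SDs are:

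- (a) √((1+ρ)/2)
- (b) √(2(1−ρ))
- (c) 1
- ANCOVA √(1−ρ²)

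The noncentrality is the target divided by SD·√(2/11), and √(2/11) = 0.426. At d = 1.2 and ρ = 0.5:

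- (a) 0.6/(0.866·0.426) = 1.62
- (b) and (c) 1.2/(1·0.426) = 2.81
- ANCOVA 1.2/(0.866·0.426) = 3.25, before a small loss for chance baseline imbalance

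Readings (a) to (c) have 20 degrees of freedom and ANCOVA has 19. Power at d = 1.2, from the noncentral t for (a) to (c) and 40,000 simulated trials per setting for ANCOVA:

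| ρ | (a) arm effect | (b) interaction | (c) prostatectomy only | ANCOVA |
|---|---|---|---|---|
| 0 | 47% | 47% | 76% | 74% |
| 0.3 | 38% | 62% | 76% | 78% |
| 0.5 | 34% | 76% | 76% | 85% |
| 0.7 | 31% | 93% | 76% | 95% |

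At ρ = 0.1 and 0.2, ANCOVA has 74% and 76%, no better than (c).

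**No patient term.** An ordinary two-way ANOVA understates the standard error of the arm effect by a factor √(1+ρ). With 40 residual degrees of freedom the critical value is 2.02. At ρ = 0.5 the test in effect uses 2.02/√1.5 = 1.65. Type I error is about 8%, 11% and 13% at ρ = 0.3, 0.5 and 0.7.

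**Choosing the term afterwards.** With a correct error term, taking the smaller p of (a) and (b) gives about 10% type I error at a nominal 5%.

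**Unequal SDs.** Change scores fix the slope on baseline at 1; ANCOVA estimates it as ρ·SD(prostatectomy)/SD(biopsy). At d = 1.2 and ρ = 0.3/0.5/0.7:

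- Biopsy SD half the prostatectomy SD: interaction 78/87/95%, ANCOVA 78/85/95%, so no gain.
- Biopsy SD double: interaction 28/34/44%, ANCOVA 78/85/95%, a gain of about 50 points.

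**The case against.** The halving needs two things 8.2 does not state: specimen as the second factor, and the arm main effect as the test. A reader might infer that the plan will estimate half the drug effect. The documents do not support that. The section 2 wording about changes, compared within and between groups, points to the interaction, which estimates the full effect. Section 6.2.1 can equally be read as a post-drug comparison between arms, which also estimates the full effect, although two-way would then be a misnomer. This objection stands, and the halving is only an illustration of reading (a).

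A reader might also infer that ANCOVA wins everywhere, or that the arm effect is always the weakest test. Neither holds. ANCOVA gives no gain over prostatectomy-only below a correlation of about 0.2–0.3. It gives none over the interaction if the biopsy SD is half the prostatectomy SD. At zero correlation the arm effect and the interaction tie. Equal SDs are not assured, since up to 12 cores are set against two 250-mg samples.

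Finally, these are secondary endpoints in a 22-man phase 0 trial, and ANCOVA does not deal with men who have no tumour left to stain. Both points are correct. They limit the weight of the concern but do not supply the missing factor or term.

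**Conclusion.** The defect is established: 8.2 names a two-factor analysis with one factor, no tested term and no within-man error term. The halving and the 8–13% type I error belong to one possible reading and are not shown to be the plan's intent.

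Replacing the ANOVA with a baseline-adjusted ANCOVA is well supported. It targets the full effect and uses a biopsy value already planned. Under the equal-SD assumptions it gains about 16, 9 and 2 points over the interaction at correlations 0.3, 0.5 and 0.7, and about 2, 9 and 19 over prostatectomy-only. The gain over the interaction ranges from none to about 50 points as the biopsy SD goes from half to double the prostatectomy SD. Every power figure rests on an assumed effect, correlation and distribution. The d/2 result for reading (a) needs only randomization and no drug effect on the pre-treatment tissue.

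**What to change.** Replace both ANOVA sentences in 8.2 with, for example: *For each marker, the per-man tumour staining score at prostatectomy will be compared between arms by ANCOVA, adjusted for the same man's pre-treatment repeat-biopsy score. The arm coefficient is the between-arm test, reported with its 95% CI. Within-arm paired changes will be reported descriptively.*

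So that this defines one analysis, also:

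- Reconcile the score: staining percentage in 8.2 against intensity times percentage in 3.1.
- Reconcile the baseline specimen, which 3.1 describes both as the repeat and as the diagnostic biopsy.
- Fix one analysis scale before staining is read; log(score + 1) is one option.
- State the significance level, the apoptosis assay to be tested, how several cores or samples become one value per man, and what is done when a baseline is missing.
- Report by arm the number of men with no residual tumour. Section 8.2 foresees them in its complete-response definition ("absence of tumor identification on standard histological analysis of the resected prostate specimens"). They have no outcome for this model, which does not handle them.

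The cost is a few sentences in 8.2 and 3.1, with no new tissue or staining. Statistically it is one degree of freedom, and about 2 points of power against prostatectomy-only if the correlation is near zero (74% against 76%).

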### Secondary Objectives

- (1) To determine whether presurgical treatment with LDE225 can exert a pathological effect on high-risk tumors (i.e. increase apoptosis, decrease proliferation).
- (2) To evaluate whether presurgical treatment with LDE225 diminishes the risk of PSA recurrence following prostatectomy.
- (3) To evaluate the safety and tolerability of LDE225 in the presurgical setting.

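### Secondary objective 2 is defined as PSA ≥0.2 ng/mL at 3 months, but the only planned between-arm PSA test is of PSA <0.1 ng/mL, which is not its complement

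*Combined protocol and SAP*

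**What the plan says.** All references are to the combined protocol and SAP.

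- **Secondary Objectives, item 2:** "To evaluate whether presurgical treatment with LDE225 diminishes the risk of PSA recurrence following prostatectomy".
- **Section 2 table, endpoint for that objective:** PSA ≥0.2 "ng/ml at 3 months following prostatectomy".
- **Section 2 table, analysis for that objective:** "Routine serum ELISA for PSA", and nothing more. The pathology entry in the same column says "Comparison performed within and between treated and untreated groups", and the toxicity entry says "Comparison of routinely collected intraoperative and post-operative data between treated and untreated groups".
- **Section 6.2.1:** "The proportion of patients with undetectable PSAs at three months will also be assessed in the two groups".
- **Section 8.2, PSA response rates:** "This will be defined as an undetectable PSA (<0.1 ng/mL) at 3 months after prostatectomy". Then: "The proportion of patients achieving a PSA response will be compared between treatment arms using the Mantel-Haenszel test".

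Standard PSA is measured at the 3-month visit (Sections 3.1 and 6.1), so the value needed for either cut-point will be available.

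**The concern.** The objective asks whether the drug lowers the risk of recurrence. That is a comparison between arms of the event defined in Section 2. The only PSA comparison with a named test uses a different event at the same visit, and Section 6.2.1 also refers only to undetectable PSA. Followed as written, the plan would report undetectable PSA by arm and leave the recurrence endpoint uncompared.

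Two things are at stake. An undetectable-PSA result could be presented as evidence on recurrence, which it does not directly measure. And because the trial is open-label (Section 3.1), two unreconciled cut-points for one objective leave room to choose between them once results are known.

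**Working it through.** **The plan's own figures.** The plan gives no assumed rate, power or sample size for any PSA endpoint. Its one calculated figure, 11 men per arm in Section 8.1, is for *Gli1*. It reproduces as 11 with the continuity-corrected two-proportion formula (10% against 70%, two-sided alpha 0.10, power 80%). It has no bearing on this point.

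**Step 1: the two events side by side.**

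| 3-month PSA (ng/mL) | Section 2 (≥0.2 = recurrence) | Section 8.2 (<0.1 = response) |
|---|---|---|
| <0.1 | no recurrence | responder |
| 0.1 to <0.2 | no recurrence | not a responder |
| ≥0.2 | recurrence | not a responder |

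The complement of ≥0.2 is <0.2, and the complement of <0.1 is ≥0.1. The definitions disagree on the middle band, so a test of one is not a test of the other.

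**Step 2: search for the missing comparison.** PSA after surgery appears in the Section 2 objectives and table, Sections 3.1 and 6.1 (timing and assay), 6.2.1 and 8.2. None compares PSA ≥0.2 ng/mL between arms.

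**Step 3: effect on the estimate.** Inputs: 11 men per arm (Section 3.1.4), all assumed to have a 3-month PSA. Let kT and kC be the men at 0.1 to <0.2 ng/mL in the LDE225 and observation arms. In each arm,

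rate(<0.1) = rate(<0.2) − k/11.

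Moving the cut from <0.2 to <0.1 therefore changes the difference (LDE225 minus observation) by (kC − kT)/11:

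- kT = 1, kC = 0: −1/11 = −9.1 points
- kT = 0, kC = 1: +1/11 = +9.1 points
- kT = kC: 0
- net imbalance of 2: 2/11 = 18.2 points in either direction
- net imbalance of 3: 3/11 = 27.3 points in either direction

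If only 10 or 9 men per arm have a 3-month PSA (assumed), each man counts for 1/10 = 10.0 or 1/9 = 11.1 points.

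**Step 4: how often the band would be occupied.** The documents give no PSA distribution. If a share g of men falls in the band (assumption), the expected number is 22g and the chance of at least one is 1 − (1 − g)^22:

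| g (assumed) | Expected men of 22 | Chance of at least one |
|---|---|---|
| 5% | 1.1 | 68% |
| 10% | 2.2 | 90% |
| 20% | 4.4 | 99% |

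These figures concern whether the band is empty, not whether it is unbalanced between arms.

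**Step 5: can the conclusions differ?** The counts here are invented and deliberately extreme. LDE225 has 7 men <0.1, 4 in the band and 0 at ≥0.2; observation has 7, 0 and 4.

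- Section 8.2 event: 7/11 against 7/11, p = 1.00.
- Section 2 event: 0/11 against 4/11. Single-stratum Mantel-Haenszel: expected count 11 × 4/22 = 2, variance 11 × 11 × 4 × 18/(22² × 21) = 0.857, chi-square (0 − 2)²/0.857 = 4.67, p = 0.031. Fisher's exact test gives p = 0.090.

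This shows that divergence is possible, not that it is likely.

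**The case against.** The strongest case on the other side is that the objective is not abandoned. Sections 6.2.1 and 8.2 agree with each other, and between them they fix the marker, visit, comparison and test; only the cut-point differs from Section 2. Section 8.2 also analyses pathological complete response, which the Section 2 table does not list, so PSA response may be an added measure rather than a substitute. The table's analysis column mixes assays with comparisons and names no statistical test for any secondary endpoint, so its silence on PSA is weak evidence by itself. The size of any effect is unknown, and this is a secondary endpoint without a power statement in a 22-man phase 0 trial.

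Most of this stands as a limit on weight. A related PSA proportion is compared, the numerical effect could be nil, and the contrast within the table only supports the point. It does not remove the fault. If PSA response is an added measure, the recurrence endpoint has no between-arm analysis. If it was meant to serve objective 2, the document holds two conflicting definitions for one objective. Both readings need a correction.

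**Conclusion.** The concern holds. The Section 2 endpoint for secondary objective 2 has no between-arm analysis anywhere in the document, and the PSA event tested in Section 8.2 is not its complement. This rests on the text alone and needs no assumption.

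The numerical consequence is (kC − kT)/11: 9.1 points per man of net imbalance if all 11 per arm are evaluable, and zero if the 0.1 to <0.2 ng/mL band is balanced. Neither kC nor kT can be estimated from the documents. The primary endpoint, the sample size and the other secondary analyses are untouched. It should be corrected before analysis, but it does not threaten the trial's main purpose.

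**What to change.** Reconcile Sections 2, 6.2.1 and 8.2 before analysis, by one of two routes.

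- **(a) Keep the objective.** Add to Section 8.2 the Mantel-Haenszel between-arm comparison of the proportion with PSA ≥0.2 ng/mL at 3 months, as the analysis of secondary objective 2. Label PSA <0.1 ng/mL as a separate supportive measure, in 6.2.1 as well.
- **(b) Keep the analysis.** Change the Section 2 objective and endpoint to undetectable PSA (<0.1 ng/mL) at 3 months, and do not describe the result as recurrence.

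Route (a) is preferable because it lets the trial answer the question it poses. Either way, state how values from 0.1 to <0.2 ng/mL are classified. Since Section 3.1.4 names no stratification factor, also say whether the test is unstratified and whether its p-value is asymptotic or exact; the illustration shows this can matter with 11 per arm.

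The cost is one or two sentences plus the written amendment that Section 9.5 requires, with ethics-committee approval where Sections 9.2 and 9.5 call for it. No new sample or visit is needed, because the same 3-month PSA serves either cut-point.

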## 1      **Background**

### 1.1      **Overview of Prostate Cancer**

Despite advances in the detection and treatment of prostate cancer, it remains the second most common cause of cancer-related deaths in the United States, killing approximately 30,000 men per year. Men with high-risk localized prostate cancer (Gleason sum 8-10, PSA >20 ng/mL, clinical stage  $\geq$ T3) account for the highest density of prostate cancer deaths and many succumb to their disease despite optimal local and systemic treatments (including surgery, adjuvant radiation therapy, androgen deprivation therapy, and chemotherapy), highlighting the need for novel prostate cancer therapies for these patients.

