After obtaining baseline laboratory and clinical values (including an ECG, PSA, hematologic, and renal and hepatic panels), men will receive oral LDE225 800 mg/day or observation daily for 4 weeks ( $\pm 3$  days) prior to prostatectomy. Patients will have a clinical visit and an ECG and laboratory testing will be performed at 2 weeks and then again at 4 weeks, including a 4-week pre-prostatectomy measurement of PSA and a blood sample to determine plasma LDE225 levels by LC-MS/MS. Previous studies using other oral Hedgehog inhibitors indicate that 4 weeks will allow time for steady-state levels of drug in the plasma and for inhibition of *Gli1* expression ([LoRusso et al. 2011](#)).

Men will undergo radical prostatectomy (with bilateral pelvic lymphadenectomy as appropriate), at which point two 250-mg biopsies of prostate tissue will be obtained, frozen and stored for analysis (including *Gli1* expression, genome-wide expression analysis, intra-prostatic LDE225 levels, Ki-67, and cleaved caspase-3) with the remainder of the prostate tissue then being formalin-fixed paraffin-embedded (FFPE) and cross-sectioned for analysis as per our standard institutional procedures.

Relative fold-changes in mRNA expression of *Gli1* will be determined by first normalizing input amounts of the preoperative biopsy and prostatectomy biopsies to the housekeeping gene *HPRT1*. IHC comparisons between diagnostic biopsy specimens and prostatectomy specimens will be made by calculating immunoreactivity scores (staining intensity  $\times$  percentage cell involvement).

Protocol Version 3: October 6, 2015

All men will receive routine post-operative care, and in addition will have ultrasensitive PSA testing at 1 and 2 months post-op followed by standard PSA testing at the 3 month visit.

Study Schema

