### **5.1.5 Permitted concomitant therapy**

Medications required to treat adverse events and manage cancer symptoms, concurrent stable disease (e.g., controlled hypertension) and supportive care agents such as erythropoietin, granulocyte growth factors, or blood transfusion, and pain medications are allowed. The patient needs to notify the investigational site about any new medications he/she takes after the start of the study medication. All medications (other than study drug) and significant non-drug therapies (including physical therapy and blood transfusions) administered after the patient starts treatment with study drug must be listed on the CRF.

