### **5.1.7 Prohibited concomitant therapy**

#### **5.1.7.1 Other investigational therapies**

Other investigational therapies must not be used while the patient is on the study. Anticancer therapy (chemotherapy, immunotherapy, biologic or radiation therapy, and surgery) other than the study treatments must not be given to patients while the patient is on the study medication. If such agents are required for a patient then the patient must be discontinued from the treatment portion of the study.

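### The 3-month PSA endpoints have no rule for men who start anticancer therapy between surgery and month 3, so a PSA suppressed by that therapy is scored as a success

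*Combined protocol and SAP*

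**What the plan says.** Secondary objective 2 is stated as "To evaluate whether presurgical treatment with LDE225 diminishes the risk of PSA recurrence following prostatectomy". Two definitions serve it:

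- Section 8.2, PSA response: "This will be defined as an undetectable PSA (<0.1 ng/mL) at 3 months after prostatectomy". The analysis is "The proportion of patients achieving a PSA response will be compared between treatment arms using the Mantel-Haenszel test".
- Section 2, objectives table: PSA ≥0.2 "ng/ml at 3 months following prostatectomy".

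Section 6.2.1 also plans to compare the proportions undetectable at three months. None of the three places mentions intervening treatment.

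On treatment after surgery, Section 3.1 says "All men will receive routine post-operative care, and in addition will have ultrasensitive PSA testing at 1 and 2 months post-op". Section 5.1.7.1 provides that anticancer therapy "other than the study treatments must not be given to patients while the patient is on the study medication". Section 1.1, in its disease background, lists treatments for high-risk men ("including surgery, adjuvant radiation therapy, androgen deprivation therapy, and chemotherapy").

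On recording, Section 5.1.5 requires that other medications and significant non-drug therapies "administered after the patient starts treatment with study drug must be listed on the CRF". The Section 6.1 schedule has medication review at screening, Day 14 and the prostatectomy visit, and none afterwards. Footnote g excuses observation-arm men from the Day 14 visit. Footnote j provides telephone or in-person contact at months 1 and 2 and an office visit at month 3.

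**The concern.** The objective asks about the effect of presurgical LDE225 on PSA recurrence. Early PSA persistence that leads to treatment is an unfavourable outcome for that objective. If the treatment works, the written rule turns this outcome into a favourable one under both definitions.

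The design leaves room for this. The added PSA results at months 1 and 2 become available before the endpoint is read, and the trial is open label, so decisions to treat could differ by arm. If therapy is not captured equally in both arms, the analyst cannot show afterwards whether it affected the comparison. With 11 men per arm, the observed proportions are in effect the result, and one or two men change them visibly.

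**Working it through.** **The plan's own figure.** The documents give no rate, power or sample size for PSA. The only figure is 11 men per arm for *Gli1* (Section 8.1: 10% vs 70%, two-sided alpha 0.10, power 80%). With mean proportion 0.40:

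n = [1.645·√(2·0.40·0.60) + 0.842·√(0.10·0.90 + 0.70·0.30)]² / 0.60² = 7.1, or 8 per arm.

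With continuity correction, n′ = (7.1/4)·[1 + √(1 + 4/(7.1·0.60))]² = 10.2, or 11 per arm. The stated size reproduces, but it says nothing about PSA.

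**Reading the rules together.**

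1. The restriction in Section 5.1.7.1 on anticancer therapy is tied to time on study medication. It lapses when dosing ends and, read literally, never applies to the observation arm. The section's separate ban on investigational therapies does not cover androgen deprivation or radiotherapy as such.
2. From surgery to month 3, treatment is routine care.
3. The month-3 PSA is classified by its value alone.
4. The CRF rule starts with study drug, which observation-arm men never take, and no medication review is scheduled after surgery.

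It follows that a man with detectable PSA at month 1 who is below 0.1 ng/mL at month 3 on therapy is a responder under Section 8.2 and recurrence-free under Section 2.

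**Size per man.** 1/11 = 9.1 points; 2/11 = 18.2; 3/11 = 27.3.

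**How many men.** The documents do not say, and zero is possible. As an assumption, let 20–30% of men have detectable early PSA (0.2 × 11 = 2.2 to 0.3 × 11 = 3.3 per arm), with a third to all of them treated and made undetectable before month 3. That is about 1–3 men, or 9–27 points. The full range is 0 to 27 points per arm.

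**Effect on the comparison.** Let p be the response rate without added therapy and s the share of non-responders made undetectable by it. Then observed rate = p + (1 − p)·s. When s is equal in both arms, the observed difference is the true difference × (1 − s). All values below are assumed.

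| True rates, control vs LDE225 | s control | s LDE225 | Observed rates | Observed difference (LDE225 − control) |
|---|---|---|---|---|
| 60% vs 80% | 0 | 0 | 60% vs 80% | 20 points |
| 60% vs 80% | 20% | 20% | 68% vs 84% | 16 |
| 60% vs 80% | 40% | 40% | 76% vs 88% | 12 |
| 60% vs 80% | 40% | 10% | 76% vs 82% | 6 |
| 60% vs 80% | 10% | 40% | 64% vs 88% | 24 |
| 60% vs 60% | 40% | 10% | 76% vs 64% | −12 |
| 60% vs 60% | 10% | 40% | 64% vs 76% | +12 |

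**In counts.** Control 6/11 vs LDE225 9/11 is a 27-point difference (Fisher p = 0.36). If three control non-responders become undetectable on therapy, it is 9/11 vs 9/11, a difference of 0. In the other direction, 8/11 in each arm with three men converted in one arm only becomes 11/11 vs 8/11. This gives Fisher p = 0.21, and about 0.07 by an unstratified Mantel-Haenszel test without continuity correction.

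**Power.** Fisher power at 60% vs 80% with 11 per arm and alpha 0.05 (assumed, since none is stated for PSA) is about 7% with no added therapy and about 3% with s = 40% in both arms.

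**The case against.** The premise is not documented. No section says that androgen deprivation or radiotherapy starts within three months of surgery, or that a month 1 or 2 PSA triggers it. Section 1.1 is background on the whole disease course, not this trial's post-operative pathway. This stands, and it is why the range must include zero.

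A reader might infer that the PSA comparison would measure post-operative treatment instead of LDE225. The documents do not support that. Equal use only dilutes a difference. A false difference needs unequal use, which open-label care permits but nothing in the text shows.

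A reader might also infer that treated controls cannot be identified. That goes too far. Section 5.1.5 is poorly worded for the observation arm but does not bar recording, Section 6.2.2 has post-operative clinic notes reviewed for peri-operative events, and contacts exist at months 1 to 3. The gap is that nothing requires systematic and equal capture.

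Counting every treated man as a recurrence is a tempting remedy, but it would mislabel a man treated for pathology alone with undetectable PSA. It would also make the unblinded decision to treat an endpoint event. Scoring PSA regardless of later therapy is a legitimate estimand, but it answers a different question from secondary objective 2, and the plan does not say that it is intended.

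Finally, the endpoint is secondary, in 22 men, with very low power. That limits the weight of the point. It does not excuse a rule that scores an unfavourable course as a success.

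**Conclusion.** The point holds as a gap in the endpoint rule. Applied as written, both PSA definitions accept a value suppressed by post-operative anticancer therapy, and the plan neither restricts that therapy between surgery and month 3 nor clearly records it in the observation arm. Each affected man is worth 9.1 points in his arm. The total lies between zero, if no one starts therapy early, and 9–27 points per arm if 1–3 men do; those counts are assumed and have no source in the documents. The direction of bias in the comparison cannot be predicted. The primary *Gli1* result uses tissue taken by the time of surgery and is untouched.

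Separately, the two definitions leave PSA from 0.1 to below 0.2 ng/mL as neither response nor recurrence. Any counting rule depends on settling that.

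**What to change.** - **Counting rule (Sections 8.2 and 2).** A man in either arm who starts post-operative anticancer therapy before the month-3 PSA is not counted as a responder, or as recurrence-free, on a PSA measured under that therapy. If his last post-operative PSA before therapy was detectable, he counts as a non-responder.
- **Remaining treated men.** If that last PSA was undetectable, or there was none after surgery, report him separately by arm. Handle him in two sensitivity analyses: once as a non-responder, and once by his last post-operative PSA before therapy where one exists.
- **Assays.** Months 1 and 2 use the ultrasensitive test and month 3 the standard one. State the cut-off that makes an early value detectable, and note the difference when reporting.
- **Recording (Section 5.1.5).** Require date and type of anticancer therapy in both arms from Day 1 to month 3, collected at the contacts already scheduled. Report the number of treated men per arm.
- **Cut-offs.** Reconcile <0.1 and ≥0.2 ng/mL between Sections 8.2 and 2.

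The cost is a few sentences and one CRF field, with no extra visit and no change to any man's care. Classification will still depend partly on open-label treatment decisions; the sensitivity analyses show how much that matters. If no man is treated early, the record will show it and the PSA comparison can be read free of this doubt.
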